# 1. Study Details and Objectives

The nSTRIDE Autologous Protein Solution (APS) Kit is designed to safely and rapidly prepare APS from a small blood sample at the patient's point of care. The APS is to be injected intra-articularly for the treatment of knee osteoarthritis (OA) and associated symptoms. This study will evaluate the effectiveness and safety of use in a knee OA population.

The primary objective of this study is to determine whether nSTRIDE APS is superior to hyaluronic acid (HA) in improving mean Western Ontario and McMaster Universities Osteoarthritis Index (WOMAC) LK 3.1 pain. The metric used will be change from baseline to 12 months post-injection. The WOMAC LK 3.1 is a validated tool used for assessing knee pain, function, and stiffness. Thus, the WOMAC is comprised of three subscales. Of the three subscales comprising the WOMAC, the mean change in pain subscale score is the primary endpoint in this study. The hypothesis is that the APS group will demonstrate greater improvement than the HA group at 12 months post-injection. Further detail on the primary hypothesis is given in Section 4.2.

The impact of the usage of APS on function will be evaluated in support of the primary analysis; however, no formal statistical test for the superiority of function will be incorporated into the study success criteria. Instead, a qualitative assessment of the changes in WOMAC Function over time for APS and Hyaluronic Acid (HA) will be discussed in order to ensure that the impact of the treatment on function is neutral or positive. Further detail on this qualitative assessment is given in Section 4.2.

Secondary objectives of this study include determining whether nSTRIDE APS is superior to HA in improving WOMAC LK 3.1 function at 12 months (as evaluated using the percentage of subjects showing at least the minimal clinically important difference (MCID)), and WOMAC LK 3.1 pain at 12 months (as evaluated using the percentage of subjects showing at least the minimal clinically important difference (MCID)), OMERACT-OARSI responder rates at 12 months, analyzing WOMAC pain and function in only the KL-II Subgroup at 12 months, evaluating superiority of APS over HA in improving Numeric Rating Scale (NRS) pain at 12 months, assessment of the changes in WOMAC Pain scores over time (baseline through 12 months), and evaluation of the usage of rescue medication within 12 months. These will be tested in a fixed sequential order pending the rejection of the primary null hypothesis.

Exploratory objectives of this study include determining whether APS is superior to HA with regards to improvement in mean EQ-5D outcomes (12 months minus baseline) and repeated measures of WOMAC Function, WOMAC stiffness, and total WOMAC score. In addition, changes in joint morphology (determined with X-ray images) will be evaluated. Subgroup analyses will be conducted to investigate whether the treatment effect varies depending on subjects' initial pain and baseline information. Analysis of exploratory endpoints will be done using alpha=0.05 with no adjustment for multiple comparisons.

A long-term follow-up phase will examine the superiority of nSTRIDE APS in the duration of the treatment effect, injection frequency, patient preferences, healthcare resource utilization, and associated costs. These endpoints will be treated as exploratory endpoints and analyses will be conducted using alpha = 0.05 with no adjustment for multiple comparisons.

Finally, the safety profile of nSTRIDE APS will be compared to HA by comparing adverse events and rates between treatment groups.

# 1.1 Background of the Study

Modalities presently available for treating early to moderate osteoarthritis are palliative, without exception [1]. The nSTRIDE APS Kit builds upon *in vitro* studies, animal studies, and a limited number of human studies designed to understand the causes of osteoarthritis. These research efforts suggest that osteoarthritis is associated with an imbalance in cytokines and growth factors [2]. This imbalance adversely affects cartilage, bone, and soft tissues.

Tissue remodeling is perpetually ongoing in the body. It is a cycle of tissue breakdown and rebuilding. In osteoarthritis, findings suggest that cytokines associated with cartilage breakdown are abnormally numerous when compared to the number of tissue-building cytokines; in particular Interleukin-1 $\beta$  (IL-1 $\beta$ ) and Tumor Necrosis Factor alpha (TNF $\alpha$ )) [3-5].

The nSTRIDE APS Kit concentrates beneficial tissue-building cytokines and growth factors present in the patients' own blood in a way designed to block the activity of cytokines that break tissues down. In particular, APS concentrates Interleukin-1 receptor antagonist (IL-1ra), soluble Interleukin-1 Receptor II (sIL-1RII), and soluble Tumor Necrosis Factor Receptors I and II (sTNF-RI and sTNF-RII) [6]. This combination of concentrated beneficial factors is intended to act antagonistically to the pro-inflammatory factors that cause cartilage degradation and inflammation of the joint (IL-1 $\beta$  and TNF $\alpha$  [7, 8]. The blockade of inflammation by APS has been demonstrated *in vitro* [9, 10].

# 1.2 Study Design

The study is a two-phase, randomized, double-blind study with a planned enrollment of 246 subjects assigned to treatment groups on a 1:1 basis. It is designed to determine whether APS provides a more effective treatment for knee osteoarthritis than HA. The study will be conducted in two phases. Phase I is the randomized, double-blind portion of the study. After each subject completes all 12 month follow-up evaluations, only subjects will be blinded to the individual treatment allocation resulting in single-blind design following 12-month follow-up time point. Subjects from both groups will be able to request additional injections of their originally assigned treatment as frequently as needed, provided they did not experience any significant clinical concerns after previous treatment administrations and are benefiting from it, as determined by the investigator. During the long-term follow-up phase (12 -60 months), subjects may also elect to cross over to the other treatment arm and receive additional injections of the other treatment as frequently as needed, provided they did not experience any significant clinical concerns after previous treatment administrations and are benefiting from it, as determined by the investigator. Subjects may only cross over from their originally assigned treatment group to the other treatment group one time during the study.

### 1.3 Randomization

Subjects will be randomized to either the APS or HA treatment group on a 1:1 basis. The subjects and investigators will both remain blinded throughout Phase I of the study. Assignment to treatment groups will be stratified by site and will use random block sizes. Specifically, designated unblinded personnel at each site will provide the masked syringe to the injecting health care provider. To protect the double-blind, the treating health care professional and evaluating health care professional will be different individuals. Assignment will not be revealed until after the blood has been drawn for nSTRIDE APS Kit processing.

The randomization plan will be produced using SAS v 9.4 or similar software. Balanced randomization with random block sizes (1:1, APS: HA) will be implemented. In the event that, post-randomization, no study treatment was given, randomization will not be reassigned; however, this case will not count toward the overall sample size. Randomization will continue with the next case enrolled until the minimum sample size is reached in both treatment groups. Randomization will be stratified by site, and each site will receive separate randomization plans using random predetermined block sizes that will remain undisclosed to the sites. The randomization file will be uploaded into the electronic data capture (EDC) system. Once the subject is enrolled into the EDC and has been identified as eligible for randomization, the randomization allocation will be visible within the EDC and viewable only by the unblinded research associate. The subject will be treated according to the contents of the displayed randomization allocation.

# 2. Analysis of Baseline Data

Analyses will be done to determine whether randomization succeeded in creating groups that were balanced with regards to key baseline characteristics. Planned tests aimed at determining this are shown in **Table 1**. All tests will be under a null hypothesis of no difference between treatment groups.

These tests are intended to be used along with the magnitude/variation as a guideline to see whether any significant baseline imbalances have occurred that would need to be taken into consideration in the analysis of outcomes.

Variable	Test	Expected Outcome
Gender	Fisher's Exact	No Statistically
		Significant Difference
Age	T-Test	No Statistically
		Significant Difference
BMI	T-Test	No Statistically
		Significant Difference
Race	Likelihood Ratio	No Statistically
	Chi-Square	Significant Difference
Baseline WOMAC Pain	T-Test	No Statistically
(Screening)		Significant Difference

#### Table 1. Randomization Verification

A table showing major and minor protocol deviations will be generated comparing frequency of the occurrence of major and minor deviations between the two treatment groups.

Use of restricted medications will be summarized by type and compared between the two treatment groups.

### 3. Subject Disposition

A subject disposition table will be created showing the number of subjects in each treatment group that completed the study, with the number of 'in window' and 'all' visits indicated. Visits occurring outside of windows are not considered to be protocol deviations, but these windows can be used for the reporting of Adverse Events and Study Terminations, as well as for patients who return for follow-up outside of the protocol assigned visit window.

Visit windows are defined in Table 2 and Table 3.

Visit	1 Month	3 Month	6 Month	12
				Month
In-Window	± 7	± 14	± 14	± 28
	Days	Days	Days	Days
Days since Injection for In-Window Visits	23-37	77-105	169-197	337-393
Days since Injection for All Visits	1-61	62-137	138-274	275-456

#### Table 2. Visit Windows

After each subject completes all 12 month follow-up evaluations, individual treatment allocation will be unblinded. From this time-point on, only subjects will be blinded to the individual treatment allocation resulting in a single-blind design during the long-term follow-up period. Long-term follow-up assessment visits will be at the following intervals:

Visit	18	24	30	36	42	48	54	60
	Month							
In-Window	± 28	± 28	± 28	± 28	± 28	± 28	± 28	± 28
	Days							
Days since	520-	703-	885-	1068-	1250-	1433-	1616-	1798-
Injection for In-	576	759	941	1124	1306	1489	1672	1854
Window Visits								
Days since	457-	640-	822-	1005-	1188-	1370-	1553-	1736+
Injection for All	639	821	1004	1187	1369	1552	1735	
Visits								

Table 3. Long-Term Visit Windows

# 4. Effectiveness Outcomes

# 4.1 General Methods

The continuous variables included in the secondary and exploratory analyses will be tested for homoscedasticity using an F test and also graphically evaluated for normality (boxplots, histograms, and/or normal probability plots). If the p-value for the F-test is less than 0.05 or the plots indicate that the data are extremely non-normal, then the T-tests indicated in **Table 4** and **Table 5** may be replaced by an appropriate alternative (Satterthwaite T-test where unequal variances are found or Wilcoxon Mann-Whitney U-test (WMW) where evidence of extreme non-normality is found).

**Table 4** and **Table 5** present a comprehensive list of all planned tests, excluding tests of imaging (which will be presented separately).

# 4.2 Primary Outcome

The primary objective of this study is to determine whether nSTRIDE APS is superior to HA with respect to the improvement in mean WOMAC LK 3.1 pain score (change from baseline to 12 months post-injection). The primary hypothesis described below will be tested along with the secondary hypotheses listed in Section 4.3 using a conventional fixed-sequence procedure [11, 12], constructed using a pre-specified order of hypotheses. These tests will be performed at the 0.05 level. If the first null hypothesis is rejected, the second test will be performed at the 0.05 level. If the first null

hypothesis is not rejected, the second test, and all subsequent tests, will be performed as exploratory analyses. Since the order of the tests is fixed a priori, and the second hypothesis is tested only if the previous hypothesis has been rejected, the principle of closed testing implies that no adjustment to control the familywise error rate is necessary. The Fixed-Sequence Method is described as an acceptable method for addressing the multiplicity problem in Section IV.C.5 of the FDA draft guidance entitled, "Guidance for Industry – Multiple Endpoints in Clinical Trials".

A two-tailed independent sample T-test will be used to test the primary endpoint.

The hypotheses will be:

H0:  $\mu_{APS} = \mu_{Control}$ 

Versus

HA: µAPS ≠ µControl

A finding of nSTRIDE APS superiority on the WOMAC LK 3.1 Pain subscale will be considered evidence of nSTRIDE APS superior efficacy, and the device will be considered more efficacious than HA for the treatment of knee pain associated with OA at 12 months post-injection.

The impact of the usage of APS on function will be evaluated as part of the primary endpoint; however, no formal statistical test will be done as a part of the study success criteria. A qualitative assessment of the changes in WOMAC Function over time for APS and HA will be discussed, in order to ensure that the impact of the treatment on function is neutral or positive. The following descriptive analyses will be performed for this assessment of function:

- (1) A graphical examination of the changes in WOMAC Function for APS and HA over time, including means and standard error bars.
- (2) Descriptive statistics for the mean changes in WOMAC Function over time, separately for each treatment group. These will include mean, median, standard deviation, minimum, maximum, and 95% confidence intervals.

For each analysis, it is expected that the changes in WOMAC function will remain neutral or increase over time within the APS group, and also that the mean changes in WOMAC Function over time will be at least nominally better for the APS group than for HA. Note that a repeated measures ANOVA will also be used to assess changes in WOMAC Function over time; this analysis will be exploratory in nature and is described in **Section 4.4**.

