# 4.3 Secondary Outcomes

Secondary objectives of this study include determining whether nSTRIDE APS is superior to HA with regard to the endpoints in **Table 4**. These tests will be performed if the primary null hypotheses have been rejected. These secondary hypotheses will be tested using a fixed-sequence procedure, constructed using a pre-specified order of hypotheses. The order is shown in **Table 4**. These tests will be performed at the 0.05 level for each consecutive test until one hypothesis is tested not significantly, after which all subsequent tests will not be performed as secondary analyses, but instead will be performed as exploratory analyses only. Since the order of the tests is fixed a priori, and each subsequent hypothesis is tested only if the previous hypotheses have been rejected, the principle of closed testing implies that no adjustment to control the familywise error rate is necessary [11].

In particular, it is hypothesized that APS is superior to HA with regard to an improvement in both function and pain; thus these comprise the first two secondary endpoints tested. The subjects showing a minimum clinically important difference (MCID) in the WOMAC Function subscale will be referred to as "MCID Function responders." The proportion of subjects showing a MCID in the WOMAC Pain subscale (i.e. "MCID Pain responders") will be tested as the second-ranked secondary endpoint.

The development of the MCIDs for Function and Pain for which a patient is designated as a "function responder" or a "pain responder" is based on the data from the PROGRESS II pilot study. It is advantageous to use this data for the following reasons:

- The MCID is very much dependent on the choice of clinical score and the scale/version of the score and the follow up time point, so the best approach is to use pilot data where these variables are the same as in the current study.
- The Progress II data allows for development of an MCID that is context-specific, as it has the same or similar patient population, time point, baseline characteristics, and baseline symptom severity as this PROGRESS V study. These factors are important to consider in establishing an MCID [13].
- The Pilot study collected a transition question in which patients could rate their improvement as "Very Much Improved", "Improved", "Minimally Improved", "No Change", "Minimally Worse", "Much Worse",

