#### 6.1 Sample Size

Data used to estimate sample size are from Zimmer Biomet study APSS-33-00, a randomized study comparing APS to saline in human subjects. This calculation assumes that hyaluronic acid will perform similarly to saline. Estimates of expected difference and pooled standard deviation from this study are shown in **Table 15**.

Group	n	Mean Improvement in WOMAC	St. Dev.	Mean Diff.	Pooled St. Dev.	Sample Size Each	Combined Plus 20% Attrition
		Palli				Group	
APS	30	7.20	3.25				
Saline	15	4.93	4.73	2.27	4.06	93	246

Table 15- Results from APSS-33-00

The calculation results in 93 per group. Results are based on a two-tailed alpha of 0.049 and statistical power of 90%.

Planned enrollment was increased to 123 per group to protect against attrition of approximately 25% in either treatment group.

<sup>1 Under the original sample size calculations, the sample size of 196 randomized (98 per group) was adjusted to accommodate potential dropout rate of approximately 20%, resulting in a total sample size of 246. This sample size

A maximum of 30 sites will participate in the study. Enrollment will be stopped at any site reaching a limit of 30% of planned study enrollment.

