#### 6.2 Interim Analysis Specification

An interim analysis is planned to formally assess the sample size calculation for this study. A designated unblinded statistician, independent from the study, will conduct the interim analysis when approximately 50% of the patients have reached the 12 month time point. The observed effect size at this interim time point will be estimated for analysis, spending 0.001 of the overall alpha-level of 0.05. This leaves 0.049 alpha for the final analysis. This is appropriate, as the study Sponsor is not expecting statistical significance, nor planning to stop the study, only to re-assess the sample size calculation. Furthermore, the effect of sample size adjustment through interim analysis has been shown to have negligible effect on Type I error rates [21].

The observed effect size at the interim time point will be used by the independent, unblinded statistician to re-calculate the sample size for the study. The effect size will not be shared with the Sponsor, only whether or not an increase in the sample size is warranted. The independent, unblinded statistician will only report to the Sponsor the sample size required for 80% and 90% power given the data to that point.

If the initial sample size is large enough to provide a minimum of 80% power (i.e.  $n \ge n^*$ ), the trial will continue until all the planned number of subjects (*n*) are recruited. Otherwise, if  $n < n^*$ , we will increase the sample size and the trial will continue until enough patients (*n*\*) have been recruited that the desired power is achieved. The final new sample size for is

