#### $n_{new}=Max(n,n*).$

Therefore, if an increase in sample size is warranted by the re-calculation of the sample size requirements at the interim time point, it will only be reported how many more subjects are required in order to meet the study endpoint at

assumed a 2-sided alpha of 0.025 and power of 0.95. Note that, in accordance with the primary hypothesis, the sample size has been re-calculated under a 2-sided alpha=0.049 (instead of 2-sided alpha = 0.025) and a power of 0.90. This results in a sample size of 93 per group, or 117 when including 20% attrition and 124 when including 25% attrition. Thus the original sample size of 246 is sufficient for testing the primary endpoint with 90% power, and accommodate almost 25% attrition.

sufficient power. The sample size will not be reduced as a result of the sample size re-calculation. The sample size will only be increased, if the reassessment is so indicated. If the reassessment does not indicate an increase in sample size, then the study will continue as originally planned.

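### SAP Section 4.2 tests the primary hypothesis at 0.05, while Sections 6.1 and 6.2 set 0.049 for the final analysis, so the primary success threshold is two different numbers

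*SAP*

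**What the plan says.** Four places in the SAP bear on the significance level.

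- **Section 4.2 (Primary Outcome).** The primary and secondary hypotheses form one fixed sequence: "These tests will be performed at the 0.05 level". It continues: "If the first null hypothesis is rejected, the second test will be performed at the 0.05 level". The primary test is a two-tailed two-sample t-test. The interim analysis is not mentioned.
- **Section 4.3 (Secondary Outcomes).** The same level is repeated for the secondary endpoints: "These tests will be performed at the 0.05 level for each consecutive test until one hypothesis is tested not significantly". The interim is not mentioned here either.
- **Section 6.2 (Interim Analysis Specification).** The effect size is estimated when about half of the patients have reached 12 months, "spending 0.001 of the overall alpha-level of 0.05". Then: "This leaves 0.049 alpha for the final analysis". The section adds that the sponsor neither expects significance nor plans to stop at that point, and that the purpose is to re-assess the sample size.
- **Section 6.1 (Sample Size) and its footnote.** "Results are based on a two-tailed alpha of 0.049 and statistical power of 90" per cent. The footnote gives the reason: "in accordance with the primary hypothesis, the sample size has been re-calculated under a 2-sided alpha=0.049".

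No sentence says that the 0.05 in Section 4.2 is the overall level before the interim spend. The protocol synopsis states the primary hypotheses without a significance level, so it does not settle the matter.

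**The concern.** The success criterion of the primary endpoint has to be a single number fixed before the data are seen. Here the section that gives the decision rule uses one number. The sections that set the alpha allocation and the sample size use another.

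Two things depend on it. The first is the superiority claim, because Section 4.2 treats a significant result on WOMAC pain as evidence of superior efficacy. The second is the status of every test in Table 4: if the primary null is not rejected, Sections 4.2 and 4.3 make all later tests exploratory. If the p-value fell between the two thresholds, someone would have to choose the governing section after seeing the result.

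The closed-testing argument in Sections 4.2 and 4.3 does not help. It explains why ordering the endpoints needs no adjustment. It says nothing about the interim look.

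**Working it through.** **Inputs from the SAP.** Overall alpha 0.05, interim spend 0.001 and final alpha 0.049 (Section 6.2). Alpha 0.05 for the primary test (Section 4.2). Two-sided 0.049, difference 2.27, pooled SD 4.06 and 93 per group (Section 6.1, Table 15). Interim at about 50% of patients (Section 6.2).

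**1. The plan's own figure.** 0.05 − 0.001 = 0.049. Section 6.2 is correct on its own terms.

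**2. Section 4.2 set against it.**

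| Final primary p-value | Section 4.2 (0.05) | Section 6.2 (0.049) |
|---|---|---|
| below 0.049 | success, sequence opens | success, sequence opens |
| 0.049 to 0.050 | success, sequence opens | failure, all later tests exploratory |
| above 0.050 | failure | failure |

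The disputed band is 0.050 − 0.049 = 0.001 wide.

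**3. Critical values.** In the normal approximation, |z| is 1.960 at 0.05 and 1.969 at 0.049. For a t-test with 244 degrees of freedom (246 − 2), the values are 1.970 and 1.978. The 244 is illustrative: Section 6.3.1 uses multiple imputation, and Section 6.2 allows the sample size to rise.

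**4. Overall type I error, three cases.**

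- *Simple addition.* 0.001 + 0.049 = 0.050, and 0.001 + 0.05 = 0.051. Addition ignores the overlap between interim and final data, so 0.051 is an upper bound.
- *Interim as a real chance to reject.* Assume 50% information, so that under the null the interim and final statistics are bivariate normal with correlation √0.5 ≈ 0.707. The overall error is 1 − P(|Z₁| < c₁ and |Z₂| < c₂), where c₁ is the two-sided 0.001 critical value. With c₂ = 1.960 (final 0.05) it is 0.0502. With c₂ = 1.969 (final 0.049) it is 0.0492.
- *No rejection possible at the interim.* The 0.001 is never used. A final test at 0.05 then gains no error from it, and 0.049 is merely conservative.

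The second and third cases leave aside any effect of the sample size increase itself, which is a separate question.

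**5. Cost in power.** With difference 2.27, SD 4.06 and 93 per group, the standardised shift is 2.27 / (4.06 × √(2/93)) = 3.81. Normal-approximation power is Φ(3.81 − 1.969) = 96.7% at 0.049 and Φ(3.81 − 1.960) = 96.8% at 0.05. These exceed the stated 90% because 93 per group does not follow from the tabled SD of 4.06. That is a separate matter: at those inputs and 90% power, the normal formula gives 68 per group under either alpha.

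**The case against.** **The interim cannot stop the trial, so no alpha is really spent.** Section 6.2 supports this to a degree: stopping is not planned, no efficacy boundary is described, and the independent statistician reports only required sample sizes. On that reading the 0.001 adds no error, and this part of the objection stands. It does not remove the conflict. Section 6.2 still assigns 0.049 to the final analysis, and Section 4.2 still uses 0.05.

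**The familywise error is 0.051.** A reader might infer this from adding the two levels. The documents do not support it as the actual error rate. It is a bound, the correlated calculation gives 0.0502, and even that needs a rejection opportunity that Section 6.2 does not describe.

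**Every test in the sequence must be at 0.049.** A reader might also infer this, since Section 4.3 says "These tests will be performed at the 0.05 level for each consecutive test" and Section 6.2 speaks of the final analysis without limiting it to the primary endpoint. The documents do not establish it. The footnote ties 0.049 to the primary hypothesis, and no section describes testing a secondary endpoint at the interim. The secondary endpoints are tested once, after primary rejection. If the primary test is controlled at 0.05 overall, testing them in order at 0.05 does not by itself inflate the familywise error. What Section 4.3 lacks is a statement of which level applies.

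**The intended level is obvious.** Sections 6.1 and 6.2 and the footnote agree on 0.049, so the intention can be inferred. That makes the repair easy. It does not make the decision rule in Section 4.2 correct as written.

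**Conclusion.** The point holds for the primary test. Section 4.2 gives 0.05; Sections 6.1 and 6.2 give 0.049 for the same final test, and no text reconciles them. This is an inconsistency between sections, not an arithmetic error: the subtraction in Section 6.2 is right.

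Its size is small: a p-value band 0.001 wide, about 0.1 percentage point of power, and an excess over 0.05 of at most 0.001 in type I error. The excess is about 0.0002 if the interim permits rejection at 50% information, and the spend contributes none if it does not. The 0.0502 and 0.0492 rest on that 50% information assumption and on a normal approximation. The reason to correct it is where it sits: on the primary success criterion and the gate to the secondary sequence.

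**What to change.** - **Section 4.2:** state that the final primary test is performed at two-sided 0.049, with a cross-reference to Section 6.2.
- **Section 4.3 and the second-test sentence in Section 4.2:** state which level applies to the secondary sequence. Using 0.049 throughout is the simple, conservative choice. Keeping 0.05 for secondary endpoints tested once, after primary rejection at 0.049, is also defensible if the SAP says so and gives the reason.
- **Sections 6.1 and 6.2:** no change to the 0.049 is needed.

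The cost is SAP wording and a slightly less favourable primary threshold. Section 6.1 already uses 0.049, so the sample size does not change. The edit should be made before the final analysis is unblinded, so that the threshold is not settled with the result in view.
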